Anaphylactic or other serious allergic reaction.	Immediately discontinue study drug and institute appropriate therapy. Participant followed until resolution or deemed medically stable by PI.
Symptoms suggestive of a lupus-like syndrome.	Discontinue study drug and institute appropriate therapy. Participant followed until resolution or deemed medically stable by PI.

9. STATISTICAL CONSIDERATIONS

Detailed methodology for summary and statistical analyses of the data collected in this study is outlined here and further detailed in a statistical analysis plan (SAP), which will be maintained by the sponsor. The SAP may modify what is outlined in the protocol where appropriate; however, any major modifications of the primary endpoint definitions or their analyses will also be reflected in a protocol amendment.

9.1. Estimands and Statistical Hypotheses

The characterization of the key estimands E1,E2,E3 that are used in the analyses are described in the [Table 3](#). The additional supportive estimands will be described in the SAP. The study objectives, endpoints and estimands are described in the [Section 3](#).

The primary (key secondary) hypothesis is that the efficacy in the combination treatment arm based on the primary (key secondary) endpoint is not superior to the efficacy of tofacitinib treatment. The primary hypothesis needs to be rejected at the one-sided significance level of 0.05 for the declaration of the superior efficacy of the particular combination treatment arm. No adjustment for the multiplicity (n=2) comparisons of the combination treatment arms with the tofacitinib treatment arm will be applied.

Table 3. Characterization of the Estimands

Notation for the Estimand	Population Targeted by the Scientific Question	Type of Endpoint	Population-level Summary for a Given Treatment	Metric for Comparison between the Treatment Groups	Account for the Intercurrent Events
E1	All treated study participants	Continuous	Mean change from baseline	Difference of mean changes from baseline	None
E2	All treated study participants	Binary	Probability of response	Ratio of probabilities of response.	None
E3	All treated study participants	Binary	Probability of response	Difference of probabilities of response	None

Other estimands may be used for assessing the robustness of results, if performed they will be documented in the statistical analysis plan. CCI

9.2. Sample Size Determination

9.2.1. Power for the Efficacy Evaluation Based on the Primary Outcome

A sufficient number of participants will be screened to achieve up to approximately 100 participants randomly assigned to the 2 combination arms and the tofacitinib monotherapy arms (the 3 arms used in primary and key secondary hypothesis testing), and up to approximately 75 participants to the PF-06650833 and PF-06651600 monotherapy arms. The dropout rate by Week 12, the time of the primary analysis, is expected to be no greater than approximately 18%, providing up to approximately 82 participants in the tofacitinib and combination arm used for the primary hypothesis testing with full 12-week data. If this drop-out rate is exceeded due to COVID-19, the proportion of participants discontinued due to COVID-19 may be replaced. The standard deviation of baseline-adjusted CFB DAS28-4(CRP) is approximately 1.20 based on prior RA studies run by the Sponsor. A pairwise comparison of a combination arm contrasted with the tofacitinib monotherapy arm using a one-sided alpha=0.05 testing level, with an assumed between-arm difference of 0.5 has a power of approximately 84%.

9.2.2. Power for the Efficacy Evaluation Based on the Key Secondary Outcome

A test of the key secondary hypothesis is based on the comparison of the proportions of study participants with DAS-28-CRP remission at Week 24. In the analysis of binary outcomes we will use the non-responder imputation treating missing value of the binary outcome as non-response with the exception of the two special cases of the reason for missing data. These special reasons for missing data include missingness related to the COVID infection (either patient illness or COVID-related problem of attending the visit) and missingness when subject attended the visit but some of the components for the calculation of the outcome (eg, ACR20) are missing. The observations that are missing for these special reasons will be excluded from the calculation of the probabilities of response at a given visit.

This strategy will make a proportion of study participants with missing values at Week 24 very small as most of the study participants with missing observations will be assigned a non-responder status. Based on historical data the remission rate for the tofacitinib monotherapy arm is assumed to be 26%. In the absence of missing observation at Week 24 a pairwise comparison of a combination arm with the tofacitinib monotherapy arm using a one sided alpha=0.05 testing level with an assumed relative remission ratio (combinations remission percentage/tofacitinib monotherapy remission percentage) of 1.7 (equivalently a combination arm remission rate of 44.2%) has a power of approximately 84%.

9.3. Populations for Analysis

For purposes of analysis, the following populations are defined:

Defined Population for Analysis	Description
Modified Intent to Treat (mITT)	Observations for participants randomly assigned to investigational product who take at least 1 dose of investigational product. Participants will be analyzed according to the randomized intervention
Safety analysis set	Observations for participants randomly assigned to investigational product who take at least 1 dose of investigational product. Participants will be analyzed according to the product they actually received.
CCI	
PD data set	Observations for participants randomly assigned to investigational product and who take at least 1 dose of investigational product and have at least 1 of PD parameters of interest. Participants will be analyzed according to the randomized intervention.

9.4. Statistical Analyses

The SAP will be developed and finalized before database lock and will describe the participant populations to be included in the analyses, and procedures for accounting for missing, unused, and spurious data. This section is a summary of the planned statistical analyses of the primary and secondary endpoints.

9.4.1. Efficacy Analyses

Endpoint	Statistical Analysis Methods
Primary: Change from Baseline DAS28-CRP at Week 12	A Mixed Model Repeated Measures (MMRM) approach to estimate the mean change from baseline of DAS28-CRP at Week 12 using data at all visits post-baseline up to Week 12 to estimate the effect of the initially randomized treatment at Week 12. The analysis will use the mITT analysis set Missing data will not be imputed for this analysis. The MMRM analysis will contain fixed effect terms for treatment, scheduled study visit, baseline DAS 28-CRP, treatment by visit interaction, baseline by visit interaction. The model will use an unstructured covariance matrix. The primary analysis, comparing the combination arm to the tofacitinib monotherapy arm will be done using estimated least squares means for each treatment arm at Week 12. The comparison will be made at the one-sided significance level of 0.05 and no adjustment for multiplicity of comparisons will be attempted.
Key Secondary: DAS28-CRP Remission at Week 24	A landmark analysis at Week 24 will estimate the relative risk of DAS 28-CRP remission comparing each combination arm to the tofacitinib monotherapy arm. This analysis will use the mITT analysis set and the non-responder imputation method (NRI). The NRI treats missing value of the binary outcome as non-response with the exception of the two special cases of the reason for missing data. These special reasons are missingness related to the COVID infection (either patient illness or COVID-related problem of attending the visit) and missingness when subject attended the visit but some of the components for the calculation of the outcome (eg, ACR20) are missing. The observations that are missing for these special reasons will be excluded from the calculation of the probabilities of response at a given visit. Exact statistical inference will be used. The comparison will be made at the one-sided significance level of 0.05 and no adjustment for multiplicity of comparisons will be attempted.
Other Secondary CCI	Will be described in the SAP finalized before database lock.

9.4.2. Safety Analyses

All safety analyses will be performed on the safety population derived from all participants enrolled.

Endpoint	Statistical Analysis Methods
Primary	
The safety data will be summarized in accordance with Pfizer Data Standards. All participants who receive at least 1 dose of IP (safety population) will be included in the safety analyses. All safety data will be summarized descriptively through appropriate data tabulations, descriptive statistics, categorical summaries, and graphical presentations. Safety endpoints for the study include:
 
 • Treatment-emergent AEs and SAEs; • Withdrawals from active treatment due to AEs; • Serious infections, defined as any infection (viral, bacterial, and fungal) requiring hospitalization or parenteral antimicrobials; • Safety laboratory tests (eg, hematology [including coagulation panel], chemistry and lipid profiles); • Vital signs; • ECG. 
Change from baseline on laboratory data, vital signs and ECG will be additionally summarized. Participant listings will also be produced for these safety endpoints.

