8.3.6.2. Opportunistic and Serious Infections

AEs of opportunistic or serious infections will be adjudicated and will have additional information requested on separate CRF pages.

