Serious infections defined as any infection (viral, bacterial, or fungal) requiring parenteral antimicrobial therapy or hospitalization for treatment or meeting other criteria that require the infection to be classified as a serious adverse event.	Treatment with all study drugs will be discontinued and the participant withdrawn from this study. Participant followed until resolution or deemed medically stable by PI.
Opportunistic infection judged significant by investigator.	Treatment with all study drugs will be discontinued and the participant withdrawn from this study. Participant followed until resolution or deemed medically stable by PI.
Other	
Participants who have a flare of RA requiring treatment with prohibited concomitant medication are to be discontinued from the study treatment.	Treatment with all study drugs will be discontinued and participants will be treated for their RA according to local standard of care (SoC) practice. Upon discontinuation of the study treatment, participants will enter a FU period of 4 weeks, after which they will complete the FU/EOS visit and will be withdrawn from the study.

Condition	Action
Participants who require additional/increased doses of pain control medication for more than 5 consecutive days for treatment of increased RA symptoms should be discontinued from the study treatment.	Treatment with all study drugs will be discontinued and participants will be treated for their RA according to local standard of care (SoC) practice. Upon discontinuation of the study treatment, participants will enter a FU period of 4 weeks, after which they will complete the FU/EOS visit and will be withdrawn from the study.
Participants who at any time from Week 12 to Week 24 do not manifest a minimal clinical response as defined by meeting ACR20 criteria.	Treatment with all study drugs will be discontinued and participants will be treated for their RA according to local standard of care (SoC) practice. Upon discontinuation of the study treatment, participants will enter a FU period of 4 weeks, after which they will complete the FU/EOS visit and will be withdrawn from the study.

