10.3.2. Definition of SAE

If an event is not an AE per definition above, then it cannot be an SAE even if serious conditions are met (eg, hospitalization for signs/symptoms of the disease under study, death due to progression of disease).

An SAE is defined as any untoward medical occurrence that, at any dose:
a. Results in death
b. Is life-threatening
The term “life-threatening” in the definition of “serious” refers to an event in which the participant was at risk of death at the time of the event. It does not refer to an event that hypothetically might have caused death if it were more severe.
c. Requires inpatient hospitalization or prolongation of existing hospitalization
In general, hospitalization signifies that the participant has been detained (usually involving at least an overnight stay) at the hospital or emergency ward for observation and/or treatment that would not have been appropriate in the physician's office or outpatient setting. Complications that occur during hospitalization are AEs. If a complication prolongs hospitalization or fulfills any other serious criteria, the event is serious. When in doubt as to whether “hospitalization” occurred or was necessary, the AE should be considered serious.
Hospitalization for elective treatment of a preexisting condition that did not worsen from baseline is not considered an AE.
d. Results in persistent disability/incapacity

 • The term disability means a substantial disruption of a person's ability to conduct normal life functions.

- This definition is not intended to include experiences of relatively minor medical significance such as uncomplicated headache, nausea, vomiting, diarrhea, influenza, and accidental trauma (eg, sprained ankle) which may interfere with or prevent everyday life functions but do not constitute a substantial disruption.

e. Is a congenital anomaly/birth defect

f. Is a suspected transmission via a Pfizer product of an infectious agent, pathogenic or non-pathogenic, is considered serious.

The event may be suspected from clinical symptoms or laboratory findings indicating an infection in a participant exposed to a Pfizer product. The terms “suspected transmission” and “transmission” are considered synonymous. These cases are considered unexpected and handled as serious expedited cases by pharmacovigilance personnel. Such cases are also considered for reporting as product defects, if appropriate.

g. Other situations:

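### Serious infection is defined more narrowly for the safety endpoint (Protocol 9.4.2) than for discontinuation (8.11), so the descriptive summary can omit infections that are SAEs on another criterion

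*Protocol*

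**What the plan says.** Protocol Section 9.4.2 (Safety Analyses) names the safety endpoints to be summarised descriptively. One of them is "Serious infections, defined as any infection (viral, bacterial, and fungal) requiring hospitalization or parenteral antimicrobials". That gives two routes into the endpoint.

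Protocol Section 8.11 (Guidelines for Monitoring and Discontinuations) also defines the term, and gives three routes: "Serious infections defined as any infection (viral, bacterial, or fungal) requiring parenteral antimicrobial therapy or hospitalization for treatment or meeting other criteria", where the last route is completed by the words "meeting other criteria that require the infection to be classified as a serious adverse event". The action attached is "Treatment with all study drugs will be discontinued and the participant withdrawn from this study".

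Protocol Section 8.3.6.2 uses the term again without defining it: "AEs of opportunistic or serious infections will be adjudicated and will have additional information requested on separate CRF pages".

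The SAP does not define serious infection. Its endpoint table (Section 2.1), its safety endpoint section (3.3) and its special-interest AE list (6.3.1) all refer to severe and opportunistic infections, as does the endpoint table in Protocol Section 3. Protocol Section 10.3.3 warns against confusing a severe event with a serious one: the first describes intensity, the second rests on the SAE outcomes.

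**The concern.** The two sections use the same label, each in the form of a definition, and the one that governs what is tabulated lacks a route that the other has. An infection that is an SAE on a ground other than hospitalisation, and that is not treated parenterally, is a serious infection under 8.11 and ends the participant's treatment. Read literally, 9.4.2 does not count it.

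The line matters because infection is a leading safety question for these drugs. Protocol Section 2.3 puts serious infection at the head of the tofacitinib risks, lists it among the potential risks of PF-06651600, and treats an effect on infection rates as possible for PF-06650833. The trial asks whether combining mechanisms keeps an acceptable safety profile, so the serious-infection counts will be read across arms. They should rest on one stated definition.

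**Working it through.** The documents give no infection rate, so there is no plan figure to reproduce. The check is a comparison of the two definitions, route by route, against the SAE criteria in Protocol Section 10.3.2.

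| Infection that… | Serious under 8.11 | Serious under 9.4.2 |
|---|---|---|
| requires hospitalisation | yes | yes |
| requires parenteral antimicrobials | yes | yes |
| is life-threatening, neither of the above required | yes | no |
| leaves persistent disability, neither of the above required | yes | no |
| results in death, neither of the above required | yes | no |
| is an SAE as a suspected transmission through a product or under the remaining SAE situations, neither of the above required | yes | no |

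**Step 1: is the third route empty?** No. Section 10.3.2 lists its criteria as alternatives. Entries such as "a. Results in death" and "b. Is life-threatening" stand on their own, without a condition of hospitalisation or parenteral treatment.

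**Step 2: does either definition contain the other?** Section 8.11 speaks of hospitalisation for treatment, while 9.4.2 says hospitalisation only. That difference does not open a gap the other way, because inpatient hospitalisation is itself an SAE criterion in 10.3.2 and so enters 8.11 by its third route. The 9.4.2 set is therefore essentially a subset of the 8.11 set. What it leaves out is the group of infections that are SAEs on a ground other than hospitalisation and are not judged to require hospitalisation or parenteral therapy.

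**Step 3: does other text close the gap?** Section 8.3.6.2 sends serious infections to adjudication but gives no definition. The SAP's severe-infection wording cannot stand in for one, because the protocol separates severity from seriousness. No section of either document reconciles 8.11 with 9.4.2.

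**Step 4: where else would the omitted event appear?** Section 9.4.2 also lists treatment-emergent AEs and SAEs, withdrawals from treatment due to AEs, and participant listings. SAP 6.3.1 likewise plans the incidence of SAEs and of AEs leading to discontinuation. The event is absent from the serious-infection line only.

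**Step 5: scale.** Protocol Section 9.2.1 plans about 100 participants in each combination arm and the tofacitinib arm, and about 75 in each of the other two arms. One omitted participant changes an arm's incidence by 1/100 = 1.0 percentage point, or 1/75 = 1.3 percentage points. This only converts one event into a percentage. It does not estimate how many events would be omitted, and the documents offer no basis for that number.

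**The case against.** The case for leaving the text alone has several parts.

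- **The event is reported anyway.** It appears among SAEs, among AE withdrawals if treatment is stopped, and in listings. This stands, and it is the main reason the point is narrow.
- **The endpoint says requiring, not receiving.** A life-threatening or fatal infection could well be judged to have required hospital care or parenteral treatment even if it was not given. This stands in part: it shrinks the omitted group, but leaves its edge to judgement and does not restore the missing route.
- **The two sections have different jobs.** A discontinuation rule may be deliberately broad and a descriptive endpoint deliberately restricted to objective criteria. That would be a fair choice if it were stated. Here the same term is defined twice with no sign that the difference is intended.
- **Section 9.4 is a summary that the SAP may modify, and the adjudication charter or the sponsor's data standards may settle the term.** Possible, but neither of those is among the documents, 9.4.2 does not defer to the charter for its definition, and the SAP has no serious-infection line. As it stands, the only explicit analysis definition is the narrower one.

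A reader might also infer stronger claims, which the documents do not support. One is that a fatal infection could vanish from the safety report: it could not, given the other summaries, and a death from an infection judged to require neither hospital care nor parenteral therapy is an edge case. Another is that emergency-room care falls in the gap: Section 10.3.2 includes detention in an emergency ward within hospitalisation, and its separate emergency-room example concerns allergic bronchospasm. A third is that infections treated orally in outpatients fall in the gap as a class: 10.3.2 names no such criterion.

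**Conclusion.** The inconsistency is real. Following 9.4.2 as written can leave out of a named safety endpoint some infections that 8.11 calls serious. The consequence is limited to one descriptive line: no test, threshold or decision rule depends on it, and the same events are visible elsewhere in the safety output.

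The size is unknown. It is probably small and may be zero, on the assumption that most serious infections are either hospitalised or treated parenterally; the documents give no rates with which to check that. A reader might infer that a substantial share of an arm's serious infections would be lost, but any such fraction would need both an assumed event count and an assumed omission.

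The conclusion rests on reading both definitions literally, and on no unseen document, such as the adjudication charter, supplying a single governing definition for the analysis.

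**What to change.** Reconcile the passages for analysis purposes only:

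1. In Protocol 9.4.2, let the serious-infection endpoint count every infection that meets the 8.11 definition, including the route through other SAE criteria.
2. In SAP 6.3.1, add a matching serious-infection line, since none exists there now, and keep it distinct from the severe-infection line.
3. Show the hospitalised or parenterally treated subset beneath the total, so that the count under the present 9.4.2 wording remains available.

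The discontinuation rule in 8.11 is unchanged, and no view is taken on it.

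The cost is one line in each document and the corresponding table specification. Protocol Section 10.3.3 already requires all SAEs to be recorded on the CRF, so the qualifying events should be identifiable from data already planned, although the CRF itself was not available to confirm the fields. The change fits before the SAP is finalised, which Protocol Section 9.4 sets ahead of database lock. The downside is that the reported count may be slightly higher.

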9.4.2.1. Electrocardiogram Analyses

Changes from baseline for the ECG parameters QT interval, heart rate, QTc interval, PR interval, and QRS complex will be summarized by treatment and time.

The number (%) of participants with maximum postdose QTc values and maximum increases from baseline in the following categories will be tabulated by treatment:

Safety QTc Assessment

Degree of Prolongation	Mild (msec)	Moderate (msec)	Severe (msec)
Absolute value	>450-480	>480-500	>500
Increase from baseline		30-60	>60

In addition, the number of participants with uncorrected QT values >500 msec will be summarized.

